### 3.1.1 Phone Calls

Site personnel will call the parents 1 month  $\pm$  1 week following the prescription of any new spectacles or after a change in spectacles. The purpose of the call is to determine whether the new spectacles have been received and are being worn, to determine whether there are any problems / symptoms with wearing the spectacles, and to determine whether the parent has any questions about the study.

### 3.2 Masking Procedures

Participants will not be masked to their treatment group, given that their spectacles either will or will not have a visible flat-top bifocal. The investigator treating each participant also will not be masked to treatment group. Therefore, an examiner masked to treatment group will measure eye alignment and stereoacuity at all follow-up visits and conduct the binocular function testing at the required follow-up visits. Masking of examiners will be accomplished in two ways. First, unmasked personnel will place painter's tape (provided to sites) over the entire lower half of the HOME spectacle lenses such that the tape covers the entire bottom half and top line of the BFL segment or where the BFL segment would be located (upper edge at mid-pupil) if the SVLs were BFLs (*see ETS3 Procedures Manual*). All distance testing and some near testing will be done through the distance correction using the top portion (above the tape) of the HOME spectacle lenses. Second, where specified, some near testing will be performed with the participant wearing their OFFICE spectacles; these spectacles remain at the study site. Masked exams will be completed at all study visits unless otherwise specified.

### 3.2.1 Masked Examiner

The masked examiner must be a pediatric optometrist, pediatric ophthalmologist, or certified orthoptist who is not aware of the participant's assigned treatment.

**3.3 Follow-up Procedures Prior to 36 Months**

The following procedures will be performed in the order specified below at each interim follow-up visit occurring at 3, 6, 9, 12, 18, 24, and 30 months, with participants wearing their HOME spectacles or their OFFICE spectacles as specified by the protocol. Participants who present for a follow-up visit without their HOME spectacles, or whose HOME or OFFICE spectacles do not meet the spectacle tolerance criteria as determined by lensometry (see below) will be tested in trial frames with the appropriate randomized refractive correction (based on the most recent cycloplegic refraction and with any allowed adjustments to the most recent prescription as outlined in sections 3.13.2 and 3.13.3) and either with or without +3.00 D added power (to substitute for OFFICE and HOME spectacles, respectively). The two sphere powers should be added and a single lens used for the spherical power component of the trial frames.

**NOTE:** Participants with confirmed failure status (sections 3.5 and 3.6) who have completed a Post-failure Secondary Outcome Visit will return for interim follow-up at 12 months and 24 months with abbreviated testing (section 3.7.2).

**1. Lensometry:**

- Spectacles (HOME and OFFICE) must meet the following spectacle tolerance criteria as compared with the participant's last prescribed refractive correction (NOTE: if the hyperopic sphere and/or bifocal add power have been reduced per protocol [see sections 3.13.2 and 3.13.3], the sphere and add power must meet the spectacle tolerance criteria as compared with what was last prescribed):
  - SE refraction must be corrected within  $\pm 0.625$  D
  - Sphere power must be corrected within 0.50 D
  - Anisometropia must be corrected within  $\pm 0.50$  D SE
  - Cylinder power must be corrected within  $\pm 0.50$  D
  - Cylinder axis must be within  $\pm 10$  degrees if cylinder power is  $\leq 1.00$  D, and within  $\pm 5$  degrees if cylinder power is  $> 1.00$  D.
  - If bifocals, bifocal must be a flat-top 35 and meet the following criteria:
    - Height must be within  $\pm 2$  mm of mid-pupil
    - Power must be within  $\pm 0.50$  D of that prescribed
    - Total sphere power of the bifocal segment must be corrected within  $\pm 0.50$  D of the sum of the prescribed bifocal power and distance sphere power
    - Measured bifocal add power (i.e., dioptric difference between distance sphere power and bifocal sphere power) must be within  $\pm 0.50$  D of prescribed bifocal add power.
- If at any follow-up visit the participant's spectacles (HOME or OFFICE) do not meet these spectacle tolerance criteria (above) based on the most recent cycloplegic refraction and with allowed adjustments to the most recent prescriptions as outlined in sections 3.13.2 and 3.13.3, then the spectacles must be remade. NOTE that if the spectacles are found to be out of tolerance at any follow-up visit, testing should be performed in trial frames rather than requiring the participant to return for another visit.

- 509 2. Diplopia Assessment: Assess diplopia presence and frequency over the last week by parental  
510 report. If present, classify diplopia frequency as “2 times or less per day” or “more than 2  
511 times per day.”
- 512 3. Monocular Visual Acuity Testing: Distance VA will be measured (right eye first) with the  
513 participant wearing their HOME spectacles and without cycloplegia, using the same test  
514 method used at enrollment.
- 515     • ATS-HOTV; e-ETDRS; OR crowded single-optotype or single-line HOTV, LEA  
516         SYMBOLS, or Snellen letters (Allen pictures and Tumbling E optotypes are NOT  
517         allowed)
- 518     • NOTE: VA testing may be performed at the end of the visit.
- 519 4. Randot Preschool Stereoacuity Test with OFFICE spectacles #1 (masked):  
520     • Tested in OFFICE spectacles at 33 cm (see *ETS3 Procedures Manual*)
- 521 5. Ocular Alignment Testing – cover/uncover test, SPCT, and PACT (masked):  
522     • Wearing OFFICE spectacles and testing at near (33 cm) only
- 523     • Wearing HOME spectacles with participant viewing **through the TOP** of the lenses  
524         (with bottom half of lenses taped) at both distance (3 m) and near (33 cm) (see *ETS3*  
525         *Procedures Manual*) \*
- 526 6. Randot Preschool Stereoacuity Test in OFFICE spectacles #2 (masked):  
527     • Tested a second time in OFFICE spectacles at 33 cm.\*
- 528 7. Additional Testing: if failure criteria are met (section 3.5) (**masked**)
- 529 8. Cycloplegic Refraction (at all 12-, 24-, and 30-month visits, and only if failure is met at any  
530 other visit):  
531     • NOTE: If failure criteria are met, the additional procedures in section 3.5.1 must be  
532         completed prior to the cycloplegic refraction.
- 533     • The cycloplegic refraction must be performed 30 to 45 minutes following at least one  
534         application of cyclopentolate 1%.
- 535     • If the cycloplegic refraction reveals uncorrected refractive error outside the spectacle  
536         tolerance criteria (above), the spectacle correction must be updated (see section 3.12).  
537         (Smaller refractive changes may be prescribed at investigator discretion). Any changes  
538         that are made to the HOME spectacles will be made to the OFFICE spectacles at the  
539         same time.

540 \*Test distance for near stereoacuity and other binocular testing is 33 cm rather than 40 cm because of the focal length of the  
541 +3.00 D add

### 542 **3.4 36-Month Primary Outcome Visit**

543 At the 36-month primary outcome visit, participants will complete the following test procedures  
544 in the order specified below (1-9) while wearing their HOME spectacles or OFFICE spectacles,  
545 as specified. Participants who present without their HOME spectacles or whose HOME or  
546 OFFICE spectacles do not meet the spectacle tolerance criteria (section 3.12) as determined by  
547 lensometry, should be tested in trial frames. The trial lenses should be the appropriate  
548 randomized refractive correction (based on the most recent cycloplegic refraction and with the  
549 allowed adjustments to the most recent prescriptions as outlined in sections 3.13.2 and 3.13.3)  
550 either with or without the added +3.00 D power to substitute for the OFFICE and HOME  
551 spectacles, respectively. The two sphere powers should be added and a single lens used for the  
552 spherical power component of the trial frames.

- 553 1. Lensometry (HOME and OFFICE spectacles)
- 554 2. Diplopia Assessment: Assess diplopia presence and frequency over the last week by  
555 parental report. If present, classify diplopia frequency as “2 times or less per day” or “more  
556 than 2 times per day.”
- 557 3. Monocular Visual Acuity Testing: Distance VA will be measured (right eye first) with the  
558 participant wearing their HOME spectacles and without cycloplegia, using the same test  
559 method used at enrollment.
- 560 4. Randot Preschool Stereoacuity Test wearing OFFICE spectacles #1 (masked): Tested in  
561 OFFICE spectacles at 33 cm (see *ETS3 Procedures Manual*).\*
- 562 5. Random Dot Stereo Butterfly Test wearing OFFICE spectacles (masked): Tested in  
563 OFFICE spectacles at 33 cm (see *ETS3 Procedures Manual*).\*
- 564 6. Preschool Worth 4-Shape test wearing OFFICE spectacles (masked): Tested in OFFICE  
565 spectacles using the hand-held Preschool Worth 4-Shape test held at 33 cm (see *ETS3  
566 Procedures Manual*).\*
- 567 7. Randot Preschool Stereoacuity Test wearing OFFICE spectacles #2 (masked): tested in  
568 OFFICE spectacles at 33 cm (see *ETS3 Procedures Manual*)\*
- 569 8. Ocular Alignment Testing - cover/uncover test, SPCT, and PACT (masked):  
570     • Wearing OFFICE spectacles and testing at near (33 cm) only  
571     • Wearing HOME spectacles with participant viewing **through the TOP** of the lenses  
572         (with bottom half of lenses taped) at both distance (3 m) and near (33 cm) (see *ETS3  
573 Procedures Manual*)
- 574 9. Distance Randot Stereotest (masked): tested **through TOP** of HOME spectacles at 3 m  
575 (with bottom half taped)
- 576 10. Randot Preschool Stereoacuity Test wearing HOME spectacles (masked): Tested in HOME  
577 spectacles with participant viewing **through the TOP** of the lenses at 33 cm\* (with bottom  
578 half of lenses taped; see *ETS3 Procedures Manual*)\*

579 \*Test distance for near stereoacuity and other binocular testing is 33 cm rather than 40 cm because of the focal length of the  
580 +3.00 D add

581 **NOTE:** Participants who meet confirmed failure criteria (section 3.5) and complete the Post-  
582 failure Secondary Outcome Exam do not complete the 36-month visit.

### 583 **3.4.1 Prescribing Bifocal Spectacles at the 36-month Primary Outcome Visit**

584 For participants who HAVE NOT failed prior to or by the end of the 36-month Primary Outcome  
585 Visit:

- 586     • Participants in the SVL group will be prescribed BFLs to be worn until the 38-month  
587 Secondary Outcome Visit.
- 588     • Participants in the BVL group will continue to wear BFLs until the 38-month Secondary  
589 Outcome Visit.

590  
591 For participants who FAIL AT the 36-month Primary Outcome Visit:

- 592 • SVL participants who meet CONFIRMED failure criteria at the 36-month visit (i.e., fail  
593 and do not require a change in spectacles) will be prescribed BFLs to be worn until the  
594 38-month Secondary Outcome Visit.
- 595 • BFL participants who meet CONFIRMED failure criteria at the 36-month visit (i.e., fail  
596 and do not require a change in spectacles) will continue to wear their BFLs until the 38-  
597 month Secondary Outcome Visit.
- 598 • Participants in both treatment groups who meet failure criteria at the 36-month visit and  
599 require a Failure Confirmation Visit (see section 3.6) because their spectacles are NOT  
600 within study tolerance will be prescribed updated spectacles according to their respective  
601 treatment group and return for a Failure Confirmation Visit.

602 BFL spectacles that are being prescribed per protocol at the 36-month Primary Outcome Visit (as  
603 opposed to being prescribed at investigator discretion) should meet the following criteria based  
604 on the participant's most recent cycloplegic refraction:

- 607 • Full correction of hyperopia/myopia
- 608 • Full correction of astigmatism
- 609 • Full correction of anisometropia
- 610 • +3.00 D bifocal add (flat top, 35 mm, segment height set mid-pupil, see *ETS3 Manual of*  
611 *Procedures*).
- 612 • Children with no refractive error (emmetropia or plano refraction) will be prescribed  
613 spectacles with plano lenses and the +3.00 D bifocal add.

614 Progressive addition lenses (PALs) are NOT allowed during the study. SVL participants will  
615 wear their newly prescribed BFL spectacles until their 38-month Secondary Outcome Visit.

617 Regardless of the correction worn, all participants return for the 38-month Secondary Outcome  
618 Visit.

### 619 **3.5 Failure Criteria**

620 Treatment failure is defined as meeting one or more of the following criteria at any follow-up  
621 visit between 3 months to 36 months inclusive:

- 622 1. Constant ET  $\geq 15\Delta$  by SPCT at distance. (NOTE: intermittent ET and esophoria of any  
623 magnitude are NOT considered failures).
- 624 2. Decrease in near stereoacuity on the Randot Preschool Stereoacuity Test (at 33 cm) of 2  
625 or more levels from baseline (see levels below) stereo or from 960" (equivalent to 800"  
626 when measured at 40 cm) at baseline to nil (*criteria not applicable if nil near stereo at*  
627 *baseline*)
  - 628 • Baseline stereoacuity is defined as the near stereoacuity performed with +3.00 D  
629 added to the participant's enrollment distance spectacle correction in trial frames.
  - 630 • At all follow-up visits, the best of two stereo measures in the OFFICE lenses will be  
631 used to determine treatment failure.
  - 632 • Stereoacuity values are calculated for the 33 cm test distance required for testing  
633 through the added +3.00 D lenses at near (instead of the standard 40 cm). **NOTE:**  
634 Participants without measurable near stereoacuity at baseline cannot fail by  
635 stereoacuity criteria.

636  
637  
638**Table 2. Baseline and Follow-up Randot Preschool Stereoacuity Test Levels for Defining Treatment Failure**

Baseline Stereoacuity (in trial frames with lens power that is +3.00D more than distance correction) a	Follow-up Stereoacuity for Treatment Failure (best of two tests in OFFICE spectacles)
48" (40" at 40 cm)	120" or worse
72" (60" at 40 cm)	240" or worse
120" (100" at 40 cm)	480" or worse
240" (200" at 40 cm)	960" or worse
480" (400" at 40 cm)	Nil
960" (800" at 40 cm)	Nil
Nil	Not applicable

639  
640  
641  
642  
643  
644  
645  
646  
647  
648  
649  
650  
651  
652  
653  
654  
655  
656  
657  
658  
659  
660  
661  
662  
663  
664  
665  
666  
667  
The two sphere powers should be added and a single lens used for the spherical power component of the trial frames.

3. Binocular diplopia with a frequency of “more than 2 times per day” over the last week by parental report.
4. If any nonsurgical or surgical treatment for ET other than the randomized treatment is started before the participant meets failure criteria, the participant will be considered a failure at the visit at which the non-randomized treatment is prescribed.

If treatment failure occurs, proceed according to whether the participant failed **PRIOR** to the 36-month Primary Outcome Visit (section 3.5.1) or **AT** the 36-month Primary Outcome Visit (section 3.5.2).

If failure has been **CONFIRMED** previously in the study, there is no need to confirm failure at subsequent visits. Participants with previously **CONFIRMED** failure will continue in follow-up as outlined in section 3.7.1 regardless of whether they meet failure criteria again on subsequent visits.

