Endpoint	
Primary Effectiveness Outcome: Treatment failure defined as meeting any one of the following criteria at any follow-up visit between 3 months to 36 months inclusive:
 
 
1. Distance motor failure: Constant ET <math>\geq 15\Delta</math> by SPCT at distance. (NOTE: intermittent esotropia and esophoria of any magnitude are NOT considered failures).
 
2. Near stereo failure: Decrease in near stereoacuity on the Randot Preschool Stereotest of 2 or more levels from baseline or from 960" at baseline to nil (criteria not applicable if nil near stereo at baseline) 
 
• Baseline stereoacuity is defined as the near stereoacuity performed with +3.00 D added to the participant's enrollment distance spectacle correction in trial frames.
 
• At all follow-up visits, the best of two stereo measures in the OFFICE lenses will be used to determine treatment failure.
 
• Stereoacuity values are calculated for the 33 cm test distance required for testing through the added +3.00 D lenses at near (instead of the standard 40 cm).
 
• NOTE: Participants without measurable near stereoacuity at baseline cannot fail by stereoacuity criteria.
 
 
 
3. Binocular diplopia with a frequency of "more than 2 times per day" over the last week by parental report
 
4. Nonsurgical or surgical treatment for ET, other than the randomized treatment, is started before a failure criterion is met
 
 
Key Secondary Effectiveness Outcomes: Binocular function test score with both groups in BFLs 2 months following failure or at the 38-month visit, if no failure (whichever comes first).
 
Key Safety Outcomes: Distance motor or near stereo failure, reduction of distance visual acuity of <math>\geq 0.2</math> logMAR

DESCRIPTION	

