### **3.5.1 Procedures for Participants Meeting Failure Criteria at a Study Visit **PRIOR** to the 36-month Primary Outcome Visit**

All participants who meet failure criteria **PRIOR** to the 36-month Primary Outcome Visit will undergo the following **additional** testing in the order specified below (1-5) at the visit when the failure criterion is met:

1. Random Dot Stereo Butterfly test (**masked**): tested in OFFICE spectacles at 33 cm.\*
2. Preschool Worth 4-Shape test (**masked**): tested in OFFICE spectacles at 33 cm.\*
3. Distance Randot Stereotest (**masked**): tested through **TOP** of HOME spectacles at 3 meters (with bottom half of lenses taped). (See *ETS3 Procedures Manual* for taping instructions)
4. Randot Preschool Stereoacuity Test (**masked**): tested through **TOP** of HOME spectacles at 33 cm (with bottom half of lenses taped) (See *ETS3 Procedures Manual*)\*
5. Cycloplegic Refraction (after the testing above is completed)

- 668     • The cycloplegic refraction must be performed 30 to 45 minutes following at least  
669       one application of cyclopentolate 1%.
- 670     • If the cycloplegic refraction reveals that the spectacles no longer meet the spectacle  
671       tolerance criteria according to section 3.12, the spectacle correction must be  
672       updated (both HOME and OFFICE spectacles).

673       \*Test distance for near stereoacuity and other binocular testing is 33 cm rather than 40 cm because of the focal  
674       length of the +3.00 D add.

675       If based on the cycloplegic refraction performed at this visit:

- 676       • The spectacle correction IS within tolerance (section 3.12) and does not need to be  
677       updated:
- 678           1. Failure is CONFIRMED at this visit.
  - 679           2. The participant should be prescribed BFLs (if in the SVL group) or continued in  
680           BFLs (if in the BFL group) (section 2.8)
  - 681           3. The participant should return in 2 months (window: 4 to 12 weeks) for their Post-  
682           failure Secondary Outcome Visit (section 3.7).
- 683
- 684       • The spectacle correction is NOT within tolerance (section 3.12) and needs to be updated:
- 685           1. Failure is NOT CONFIRMED at this visit.
  - 686           2. The participant should be prescribed new spectacles (according to the criteria in  
687           section 2.8) consistent with the participant's randomized group assignment to SVL  
688           or BFL spectacles.

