### 875     **3.10 Initiating Non-randomized Treatment for Esotropia (ET)**

876     Non-randomized treatment for ET is NOT permitted during the study unless the following 3  
877       conditions have been met:

- 878       1. Participant has met failure criteria (section 3.5)

- 879        2. Failure was confirmed either at the initial visit (section 3.5) or at the Failure  
880        Confirmation Visit (section 3.6)  
881        3. Participant has completed their Post-failure Secondary Outcome Visit (section 3.7).

882        If none of the failure criteria are met but the participant is experiencing overwhelming social  
883        concerns or significant symptoms (*other than frequent or constant diplopia at distance or near,*  
884        *which is a failure criterion*) associated specifically with the ET, the investigator **must call one of**  
885        **the Protocol Chairs** to discuss the case and obtain approval for an exception prior to initiating  
886        any non-randomized treatment for ET.

887        To the extent possible, participants for whom non-study treatment is planned (after discussion  
888        with Protocol Chair) should proceed as if one of the three protocol-specified failure criteria were  
889        met. Thus, they should complete the additional testing in section 3.5.1 (including the cycloplegic  
890        refraction) and a Post-failure Secondary Outcome Visit (section 3.7) prior to initiating any non-  
891        study treatment. The SVL participants will be prescribed BFL spectacles to be worn prior to the  
892        Post-failure Secondary Outcome Visit and the BFL participants should continue wearing BFLs.

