## 1198 **7.6 Analysis of Primary Outcome – Treatment Failure by 36 Months**

1199 There may be participants who are lost to follow-up before their 36-month primary outcome data  
1200 are collected. To use the data collected from these participants before they are lost to follow-up,  
1201 a time-to-event analysis will be performed for the primary outcome. For participants who meet  
1202 failure criteria before or at the 36-month Primary Outcome Visit, time to treatment failure will be  
1203 defined as the time from randomization to the visit at which the failure is confirmed (either at the  
1204 initial visit or later at a Failure Confirmation Visit because the spectacle correction must be  
1205 updated [section 3.6]). If a participant is prescribed non-randomized treatment for ET before  
1206 meeting failure criteria, they will be considered a failure at the time when such treatment is  
1207 prescribed. Participants lost to follow-up are considered censored at the time of their last  
1208 recorded visit. If a participant is lost to follow-up before failure is confirmed, they will be  
1209 censored at their last visit for the primary analysis.

1210 The hazard ratio of treatment failure for treatment with BFLs versus SVLs and a two-sided 95%  
1211 confidence interval (CI) will be estimated with a Cox proportional hazards model. The model  
1212 will be adjusted for baseline near stereoacuity by the Randot Preschool Stereotest (RPS) in +3.00  
1213 D trial frames and baseline magnitude of the distance esodeviation by SPCT. The treatment  
1214 group difference in the probability of failure and a two-sided 95% CI will be estimated using the  
1215 direct adjustment method. The proportional hazards and functional form assumptions will be  
1216 evaluated.

1217 The timing and composition of failures (distance motor, near stereoacuity, diplopia, starting non-  
1218 protocol treatment) will be tabulated by treatment group to aid in the interpretation of the  
1219 treatment group difference for failure probability by 36 months.

1220 **7.6.1 Sensitivity Analyses for Primary Outcome**

1221 As a sensitivity analysis, if a participant meets the failure criteria prior to a required spectacle  
1222 update but is lost to follow-up before the failure is confirmed, the participant will be treated as a  
1223 failure at the time when they initially met the failure criteria (suspected failure). The primary  

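### Criterion 4 stops at criteria met while the primary analysis counts failures confirmed, so esotropia treatment started between the two may go uncounted

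*Protocol*

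**What the plan says.** Starting esotropia treatment other than the assigned lens is itself a failure criterion, limited by timing in each place where the protocol states it:

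- Protocol Summary, Endpoint, item 4: "Nonsurgical or surgical treatment for ET, other than the randomized treatment, is started before a failure criterion is met".
- Section 3.5, item 4: "If any nonsurgical or surgical treatment for ET other than the randomized treatment is started before the participant meets failure criteria", the child counts as a failure, dated at the visit where that treatment is prescribed.
- Section 7.2 repeats the limit after its three numbered criteria.
- Section 7.6: "If a participant is prescribed non-randomized treatment for ET before" "meeting failure criteria, they will be considered a failure at the time when such treatment is" prescribed.

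Separately, the protocol has a confirmation step. Under 3.5.1 and 3.5.2, a child who meets a criterion but whose spectacles are out of tolerance receives updated spectacles of the assigned type and returns in 4 to 12 weeks. For a visit before 36 months the text says "Failure is NOT CONFIRMED at this visit", and 3.5.2 says the equivalent for 36 months. Section 7.6 dates the failure at the confirming visit.

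Section 3.10 prohibits non-randomized treatment until three conditions hold. Meeting the criteria is the first. Confirmation is listed separately as the second ("Failure was confirmed either at the initial visit (section 3.5) or at the Failure" Confirmation Visit). The third is completion of the post-failure visit.

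**The concern.** Criterion 4 exists to classify children whose treatment departs from the plan. As worded, it stops applying when a criterion is met, but the event in the primary analysis does not exist until failure is confirmed. The interval between the two has no outcome rule for off-plan treatment.

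A child who worsened enough to meet a criterion, then received another esotropia treatment, and then tested better could be carried as a non-failure of the assigned lens. Treating investigators and families are unmasked (3.2), so the frequency of such treatment could differ between arms. The planned event count is small, so individual classifications matter.

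**Working it through.** This is mainly a question of tracing the rules. Take a child who meets the distance motor criterion at a visit before 36 months and whose spectacles prove to be out of tolerance.

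1. **Is the suspected failure an event?** Not in the primary analysis: 3.5.1 leaves it unconfirmed, and 7.6 needs confirmation. The synopsis, 3.5 and 7.2 define failure as meeting a criterion at any visit, with no confirmation step. The non-failure result therefore comes from 3.5.1, 3.5.2, 3.6 and 7.6.
2. **How long is the gap?** The target is 60 days. The allowable window in the 3.1 table runs from 30 days with no upper limit.
3. **Other esotropia treatment starts in the gap. Does criterion 4 apply?** Literally no, because a criterion has already been met.
4. **No criterion is met at the Failure Confirmation Visit.** Section 3.6 sends the child back to scheduled follow-up. If the suspected failure was at 36 months, the child goes on to the 38-month visit.
5. **First sensitivity analysis (7.6.1).** It counts a suspected failure only if the child is lost before confirmation. This child returned.
6. **Second sensitivity analysis (7.6.1).** It concerns crossovers before any clinical failure measure is met, and it censors them. This child had already met one.
7. **Objective 1 (1.9).** It lists undergoing non-study treatment as failure with no timing limit. The operational rule is narrower than the objective.

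**Does the wording settle what meet means?** No.

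| Place | Use |
|---|---|
| 3.5.1, 3.5.2, 3.10 | Met and confirmed are separate states |
| 3.4.1 | Adds the word confirmed when confirmed failure is intended |
| 3.1 table, footnote g; 7.7.1 | Meeting criteria leads straight to bifocals and the post-failure visit, which 3.5.1 allows only after confirmation |
| 7.6, time-to-failure sentence | Those who meet criteria are dated at the confirming visit |

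**Scale.** The plan's sample size reproduces. With 5% vs 15%, two-sided alpha 0.05, design power 90% and pooled variance:

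n = [1.960 × √(2 × 0.10 × 0.90) + 1.2816 × √(0.05 × 0.95 + 0.15 × 0.85)]² / 0.10² = 187.05, so 188 per group and 376 in total. Then 188 / 0.85 = 221.2, so 222 per group and 444 in total. This point does not change that number.

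Expected failures at full enrollment are 0.05 × 222 = 11.1 (SVL) and 0.15 × 222 = 33.3 (BFL). One misclassified child shifts the crude difference by 1/222 = 0.45 points, or by 1/188 = 0.53 points among 188 evaluable.

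**Direction.** As an assumption only, let 10% of one arm's failures go uncounted:

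- SVL only: 15.0 − 4.5 = 10.5 points, wider than the planned 10.
- BFL only: 13.5 − 5.0 = 8.5 points, narrower.
- Both arms: 13.5 − 4.5 = 9.0 points.

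**The case against.** The strongest reply is that meeting failure criteria can be read as meeting them with confirmation, as in footnote g of the 3.1 table, 7.7.1 and the neighbouring sentence of 7.6. On that reading criterion 4 catches the child. This stands as a reason to call the text ambiguous. It does not settle the matter, because 3.10 lists the two states separately.

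Second, the route needs a prohibited act plus several coincidences. Any criterion is enough to confirm failure, and a child not confirmed before 36 months can still fail later. This stands as a reason to expect few cases. Even so, 3.10 assigns no outcome to a breach, the intention-to-treat set in 7.5 keeps these children, and a child first suspected at 36 months has no later scheduled visit at which to fail. In addition, footnote b of the 3.1 table, read alone, has SVL children prescribed bifocals at the end of the 36-month visit, excepting only those released after an earlier failure. Sections 3.4.1 and 3.5.2 keep unconfirmed failures in their assigned type. Those passages must be reconciled.

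Third, a reader might infer a loss of power, or a bias favouring SVLs because section 1.7 reports that at least 75% of network providers use bifocals. The documents support neither inference. They give no rate for this event. If SVL children were the ones switched, the lost SVL failures would widen the expected difference. Moreover, distance alignment is tested through the taped top of the HOME lenses and near stereoacuity in the OFFICE lenses, so an off-protocol add does not change the test optics for those two criteria. Only carry-over from wear could affect them. Parent-reported diplopia is not protected in this way.

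A reader might also infer that one unconfirmed failure switches criterion 4 off for the rest of follow-up. The text does not say so, and 3.6 returns the child to ordinary follow-up.

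**Conclusion.** The point holds as a gap or, at best, an ambiguity in a rule of the primary endpoint. On the literal wording, a suspected failure who starts other esotropia treatment and then meets no criterion at the Failure Confirmation Visit can be a non-failure in the primary analysis and in both sensitivity analyses, contrary to Objective 1.

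The number of such children cannot be derived from the documents and should be small. The per-child shift of 0.45 to 0.53 points assumes 222 or 188 children per group and a crude difference in proportions. Bias could go either way, so no power loss should be attached to this point. The planned sample size is unaffected.

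**What to change.** Change outcome classification only:

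- In the Protocol Summary, 3.5 item 4, 7.2 and 7.6, make the trigger treatment started before failure is confirmed. The sentence in 7.2 also lacks its verb and can be repaired at the same time.
- Date the failure at the visit at which the treatment is prescribed, and state that a later Failure Confirmation Visit does not reverse it.
- Say explicitly that bifocals prescribed under the protocol at or after the 36-month visit do not trigger criterion 4, so that the new wording does not sweep in SVL children who have not failed.
- In 7.6.1, move the crossover rule to the same boundary, and state how a crossover between suspected and confirmed failure is handled.

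The cost is a few phrases in five places, with no new visits, data or participants. The edit makes no change to how children are treated.
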